- all NHS staff providing health care to an individual to access all their clinically identifiable NHS data without multiple consents;
- all NHS-approved researchers conducting healthcare research to see all relevant deidentified NHS data without multiple approvals;
- all NHS-approved researchers conducting healthcare research to see all relevant NHS health data from consenting patients and write to individuals about studies in which they may wish to participate.

There is also a lack of information on public attitudes to data sharing in relation to mental health specifically. In late 2018 the Wellcome Trust and Understanding Patient Data conducted a thorough literature review of public attitudes to patient health data use for research ¹⁷. They noted that there were few studies relating to acceptability of sharing patient health data for groups with specific health conditions, but that sharing some types of sensitive data (on mental health, sexual health, sexuality, religion, etc.) held greater concern than for other types of data. It is also the case that mental illness is subject to significant stigma ²³. Nonetheless, many psychiatric disorders convey massive loss of life expectancy via physical illness ²⁴, making the need for optimal physical healthcare in mental disorders critical and emphasizing the need for research in this area. Our project will therefore include questions about sharing mental and physical health data, for both clinical and research settings.

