1.5 Study outline

This study therefore aims to seek current patient and public views on sharing NHS/HSC identifiable health data across the UK by means of a national survey (Appendices 1-3). Views will be sought on patient and public current understanding of health data sharing, how they would like to see their identifiable health data shared (or not), with whom they would want their data shared (identifiably for clinical purposes, or in de-identified fashion for research purposes), whether they would be willing to share their mental and physical health data equally, and whether different thresholds should apply to "free text" (narrative) versus structured data. Ideas on designing a single consent form will be sought, so that identifiable health data may be shared across the UK, as well as how sign up to this might be achieved. Finally, views will be sought on data linkage for research, and on a national web portal to sign up to be contacted about health research.

For part of the survey, we will superimpose a randomised intervention, namely a framing statement, prior to seeking views relating to the sharing of mental versus physical health data. The framing statement will be one of three true statements: a "security" framing emphasising previous work reporting greater concerns about sharing mental health data versus other kinds of health data; a "neutral" statement; and a "holistic" framing emphasising the interrelationship between mental and physical illness.

This study is funded by the UK Medical Research Council (MRC) via a Mental Health Data Pathfinder (MHDP) Award (MC_PC_17213) and our CLIMB project team (Clinical Informatics for Mind and Brain Health; https://www.climbproject.org.uk/) is working together with other UK MDHP sites. This work is within the patient/public engagement workstream of that grant.

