2.2 Secondary Objectives

a) To establish if opinions on sharing mental versus physical health data are affected by the "framing" of risk versus benefit, testing the hypothesis that a "security"-focused framing statement will increase reluctance to share mental (versus physical) health data regardless of purpose and a "holistic" framing statement will have the opposite effect.

b) To propose a design of a national consent form governing NHS data sharing and seek views on it.

c) To seek public views on a national web portal to sign up for mental health research.

d) To examine views on "trusted third party" linkage followed by de-identification for research, between health data and a range of other UK state-held information sources.

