8765432109	Miss	Alice	Jones	16 Jun 1994	15 The Road, Dundee	depression carpal tunnel syndrome	2 Apr 2019. Alice's rates her mood as 1/10 on average, she is more tired, and she is not looking forward to anything. Her depression has worsened. She wishes to restart citalopram.
7654321098	[name]	4 May 1930	5 Tree Close, Cardiff	broken humerus anxiety	3 Apr 2019. Chloe fell after skidding on an oily patch while cycling and was hit by a car. Has an obvious fracture of her left upper arm. Needs X-ray.
6543210987	[name]	22 Sep 1973	27 The Mews, London	schizophrenia diabetes	4 Apr 2019. Pradeep still worries that other people can hear his thoughts, but this is getting less common. He is attending cognitive-behavioural therapy sessions.

[Participants will now randomised to see one of the following three framing questions]

Previous surveys have found that people have more concerns about the use of their identifiable health data relating to their mental health than other aspects of their physical health care.

or

We would like to find out your perspective on using information about your mental health and your physical health.

or

Mental and physical illnesses overlap, so holistic health care is important. Mental health problems have physical consequences, and physical illnesses have important consequences for mental health.

Q5
Regardless of whether you have a physical health condition or have used physical health services:

How likely are you to agree to share your identifiable PHYSICAL health data for your clinical care with the following, without being asked every time?

Sharing Physical Health Data	Very Likely	Likely	Not Sure	Unlikely	Very Unlikely	Prefer not to say
Between my local NHS services i.e. between my local physical and mental health hospitals, my GP, etc.						
Any part of the NHS in my region (cluster of hospitals nearest to my local hospital)						
Any part of the NHS in my home nation only (i.e. only in England, or only in Northern Ireland, or only in Scotland, or only in Wales)						
Any part of the NHS in the UK						

Q6

Regardless of whether you have a mental health condition or have used mental health services:

How likely are you to agree to share your identifiable MENTAL health data for your clinical care with the following, without being asked every time?

Sharing Mental Health Data	Very	Likely	Not	Unlikely	Very	Prefer
	Likely		Sure		Unlikely	not to
						say
Between my local NHS services i.e.						

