between my local physical and mental						
health hospitals, my GP, etc.						
Any part of the NHS in my region (cluster						
of hospitals nearest to my local hospital)						
Any part of the NHS in my home nation						
only (i.e. only in England, or only in						
Northern Ireland, or only in Scotland, or						
only in Wales)						
Any part of the NHS in the UK						

In the next two questions we would like to ask you about sharing your NHS data for research purposes. Research is used to improve overall healthcare for everyone.

Firstly, please look at some of the NHS health care data that you saw previously, which has now been de-identified.

Research ID	Age	Sex	Region	Diagnoses
5X62V	69	М	Kent	pneumonia
				high blood pressure
597PT	24	F	Dundee	depression
				carpal tunnel syndrome
8HG7S	89	F	Glamorganshire	broken humerus
				anxiety
BA6A9	45	М	London	schizophrenia
				diabetes

This type of data is often used for health research. The data still relates to individual people, but information that can identify a person has been removed. The data must still be kept securely, as it still contains details about an individual.

Q7

How likely would you be to share your de-identified PHYSICAL health data with the following, without giving consent every time:

Physical health	Very	Likely	Not	Unlikely	Very	Prefer
	Likely		Sure		Unlikely	not to
						say
Any part of the NHS doing research						
Academic institutions doing research						
(e.g. universities)						
A national charity doing research (e.g.						
MIND, Cancer Research UK, British						
Heart Foundation)						
A profit-making company doing						
research into treatments (e.g. a						
pharmaceutical company, health						
technology company)						
A profit-making company doing other						
research (e.g. an insurance company,						
broadband provider)						
Publicly						

Q8

How likely would you be to share your de-identified MENTAL health data with the following, without giving consent every time:

Mental Health	Very Likely	Likely	Not Sure	Unlikely	Very Unlikely	Prefer not to say
Any part of the NHS doing research						
Academic institutions doing research (e.g. universities)						
A national charity doing research (e.g. MIND, Cancer Research UK, British Heart Foundation)						
A profit-making company doing research into treatments (e.g. a pharmaceutical company, health technology company)						
A profit-making company doing other research (e.g. an insurance company, broadband provider) Publicly						

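### The security framing statement is limited to identifiable data, so an absent or smaller framing effect on the de-identified research questions could not be attributed to the research purpose

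*Protocol*

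**What the plan says.** Secondary objective (a) in Protocol section 2.2 predicts that the security statement will "increase reluctance to share mental (versus physical) health data regardless of purpose", and that the holistic statement will do the opposite.

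Section 1.5 describes the security frame as "emphasising previous work reporting greater concerns about sharing mental health data versus other kinds of health data". Section 6.3 describes it in nearly the same terms. Neither limits it to identifiable data. Section 1.4 summarises the prior work in general terms too: a review of attitudes to data use for research found that some sensitive types of data, mental health among them, "held greater concern than for other types of data".

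The statement printed in Appendix 3 is narrower: "people have more concerns about the use of their identifiable health data relating to their mental health" than about their physical health care. The neutral alternative reads "We would like to find out your perspective on using information about your mental health and your physical health". The holistic alternative is about the overlap of mental and physical illness and does not mention identifiability.

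The instruction "Participants will now randomised to see one of the following three framing questions" stands after a table of identifiable records and directly before Q5 and Q6, which concern identifiable data for clinical care. As printed, the statement is not shown again. Q7 to Q10 concern de-identified data for research; Q8, for example, asks "How likely would you be to share your de-identified MENTAL health data with the following".

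**The concern.** The hypothesis spans clinical and research use, but the security statement delivered to respondents speaks of one kind of data only. Respondents are likely to notice the limit: the survey defines identifiable health data at the start, shows an example immediately before the framing, and tells them before Q7 that identifying details have been taken out.

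Suppose the security arm shows more reluctance on mental than physical data in Q5 and Q6, but little or none in Q7 to Q10. The natural report would be that framing matters for clinical sharing and not for research sharing. The same pattern would arise if respondents simply took the statement not to apply to de-identified data, or if its influence had faded by then. The design cannot tell these explanations apart.

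**Working it through.** **1. How much of the outcome set is affected.** Rows counted from Appendix 3:

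| Questions | Data and purpose | Rows | Primary measures (section 6.3) |
|---|---|---|---|
| Q5, Q6 | identifiable, clinical care | 4 + 4 = 8 | (a), (b) |
| Q7, Q8 | de-identified structured, research | 6 + 6 = 12 | (c), (d) |
| Q9, Q10 | de-identified free text, research | 6 + 6 = 12 | (e), (f) |

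The total is 8 + 12 + 12 = 32 rows, of which 24 concern de-identified data: 24/32 = 75%. The hypothesis is about mental versus physical data, so matched pairs can be counted instead. There are 4 clinical pairs and 6 + 6 = 12 research pairs, and 12/16 is again 75%.

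**2. What varies together with purpose.**

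| | Clinical (Q5, Q6) | Research (Q7 to Q10) |
|---|---|---|
| Data | identifiable | de-identified |
| Within the literal scope of the security statement | yes | no |
| Position | directly after the statement | after Q5 and Q6 and one new table (Q7, Q8); after a further table and a re-identification warning as well (Q9, Q10) |

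Purpose, type of data, match with the statement and distance from it change together. A difference in the framing effect between the two blocks cannot be assigned to any one of them.

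**3. What each result would mean.** Allocation is randomised (section 6.2), and the intervening material is the same in all arms. The arm comparison on Q7 to Q10 is therefore an unbiased estimate of the effect of this particular statement. A security effect there would support the hypothesis despite the narrow wording. Only an absent or smaller effect is ambiguous.

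**4. Is it a question of power?** Section 6.1 gives power 0.9, f = 0.1, three groups and n = 1,269. Alpha is not stated. With a one-way analysis of variance, equal groups, noncentrality N × f² and degrees of freedom 2 and N − 3, alpha 0.05 gives N × f² = 1,269 × 0.01 = 12.69 and power 0.9001. The stated figure is reproduced exactly.

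The documents do not say how much of the effect would carry over to Q7 to Q10, so the shares below are assumptions:

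| Share of f = 0.1 retained | f | Power at 1,269 | Power at 20,000 |
|---|---|---|---|
| 100% | 0.100 | 0.90 | 1.00 |
| 75% | 0.075 | 0.66 | 1.00 |
| 50% | 0.050 | 0.34 | 1.00 |
| 25% | 0.025 | 0.11 | 0.90 |

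At the stated minimum a diluted effect could easily be missed. At the 20,000 expected in section 6.1 it would probably be found, but its smaller size would be just as hard to interpret. The weakness lies in what the statement measures, and a larger sample does not remove it.

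**The case against.** The strongest reply is that randomisation protects the comparison, that a single exposure is a legitimate design choice, and that framing is a secondary measure in section 6.3. All of that stands, and it limits the point to the interpretation of an absent or smaller effect.

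The mismatch is also less clean than a row count suggests. Before Q9 and Q10, respondents are warned that free text carries some risk of re-identification and are given an example. Concern about identifiability is therefore relevant to 12 of the 24 research rows, even though the data remain de-identified. The holistic statement, for its part, refers to health care and so leans towards clinical use. Changing one word in the security statement will not make the arms equal in scope.

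A reader might infer that the research half of the hypothesis cannot be answered at all. The documents do not support that, because a positive effect on Q7 to Q10 would be evidence for it. A reader might also average all 32 rows and conclude that some 20,000 respondents are needed. The protocol plans no such average. It would mix mental and physical rows when the hypothesis contrasts them, and the figure requires perfectly correlated rows.

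Finally, the source behind the statement is not available here. Section 1.5 requires the statements to be true, and section 1.4 does not say whether the reported concerns were about identifiable or de-identified data. The broader wording agrees with the protocol's own summary, but only the sponsor can check it against the source.

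**Conclusion.** The point holds as a mismatch between the intervention as described and the intervention as delivered. The security statement is narrower than sections 1.5 and 6.3 say and narrower than objective 2.2(a) needs. Four of six primary measures, 75% of the rating rows, lie outside its literal scope. The consequence is confined to one secondary hypothesis: an absent or smaller security effect on Q7 to Q10 should not be read as evidence that framing leaves research sharing unaffected. The arm comparison remains unbiased, a positive effect remains informative, and the descriptive aims do not depend on this wording.

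The conclusion assumes that the survey ran as printed in Appendix 3, with one showing of the statement. How far the wording would weaken the effect is unknown.

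**What to change.** **Before launch:** delete the word identifiable from the security statement, so that it agrees with sections 1.5 and 6.3 and with the summary of prior work in section 1.4. The sponsor should first confirm that the broader sentence is true to its source. The cost is one word and one check. Type of data and distance from the statement will still vary with purpose, so a smaller effect on Q7 to Q10 will still need careful wording, but the literal mismatch will be gone.

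**If the survey is already in the field** (Appendix 3 gives a live link): keep the wording, since a change midway would create two versions of the intervention. Restrict the confirmatory framing claim to Q5 and Q6, report Q7 to Q10 as carry-over from a statement about identifiable data, and do not conclude from a null there that framing has no effect on research sharing. The cost is a narrower claim.

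Repeating the statement before Q7 and Q9 is not recommended. With balanced allocation, about two-thirds of respondents would read a non-neutral prompt directly before primary measures (c) to (f), in order to strengthen a secondary test.

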1. BACKGROUND AND RATIONALE

In summary, this study is an online anonymous survey of public opinion on the ways in which national health service data should be shared between health providers or restricted: (a) identifiably, for direct clinical care of patients; and (b) in de-identified fashion, for research. We seek also to learn whether the public holds different views about the sharing of mental versus physical health data, and, in the context of research, about structured versus "free text" (narrative) de-identified data. We aim to seek views on a generic tiered consent form that could be used widely across UK national health service providers and other partners. Finally, views will be sought on data linkage for research, and on a national web portal to sign up to be contacted about health research.

In this section we describe forms of health data, set out the current situation pertaining to data sharing in the UK, summarize previous work on public opinion, and set out the rationale for our proposed study.

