The final question in this section relates to sharing de-identified "free text" data for research.

Here is the table of de-identified health care data you saw earlier, but this time a column labelled "Notes" has been added. This is known as "free text" data.

Research ID	Age	Sex	Region	Diagnoses	Notes
5X62V	69	М	Kent	pneumonia high blood pressure	1 st April 2019. XXX has a fever and cough. His chest sounds crackly. I think he has pneumonia. Sent to hospital.
597PT	24	F	Dundee	depression carpal tunnel syndrome	2 nd April 2019. XXX rates her mood as 1/10 on average, she is more tired, and she is not looking forward to anything. Her depression has worsened. She wishes to restart citalopram.
8HG7S	89	F	Glamorganshire	broken humerus anxiety	3 rd April 2019. XXX fell after skidding on an oily patch while cycling and was hit by a car. She has an obvious fracture of her left upper arm. She needs an X-ray.
BA6A9	45	м	London	schizophrenia diabetes	4 th April 2019. XXX still worries that other people can hear his thoughts, but this is getting less common. He is attending cognitive-behavioural therapy sessions.

Like the last example the data remains de-identified but gives the researchers more information. As there is more information there is a slightly increased risk of someone being identified from the data.

For example, in the table above, an "89-year-old cyclist skidding on oil and being hit by a car" may be reported in a local newspaper. Whilst the lady is not named in the data above, she would almost

certainly be named in the newspaper and it may therefore be possible for researchers to work out who she is.

Q9

How likely would you be to share your FREE TEXT de-identified PHYSICAL health data with the following, without giving consent every time:

Physical Health	Very Likely	Likely	Not Sure	Unlikely	Very Unlikely	Prefer not to say
Any part of the NHS doing research						,
Academic institutions doing research (e.g. universities)						
A national charity doing research (e.g.						
MIND, Cancer Research UK, British Heart						
Foundation)						
A profit-making company doing research						
into treatments (e.g. a pharmaceutical						
company, health technology company)						
A profit-making company doing other						
research (e.g. an insurance company,						
broadband provider)						
Publicly						

Q10

How likely would you be to share your FREE TEXT de-identified MENTAL health data with the following, without giving consent every time:

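### In survey questions Q5-Q10 the physical grid always comes just before its mental counterpart, so the descriptive mental-versus-physical contrast cannot be separated from question order

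*Protocol*

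**What the plan says.** The Protocol states the comparison as an aim in two places. Section 1 (Background and rationale) says: "We seek also to learn whether the public holds different views about the sharing of mental versus physical health data". Section 1.5 (Study outline) adds that views will be sought on "whether they would be willing to share their mental and physical health data equally".

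Section 6.3 lists six primary measures that form three physical/mental pairs: (a)/(b) for clinical care, (c)/(d) for structured research data and (e)/(f) for free-text research data. Secondary objective (a) in section 2.2 concerns the effect of framing on the same contrast: "To establish if opinions on sharing mental versus physical health data are affected by the 'framing' of risk versus benefit".

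Appendix 3 collects these measures as follows.

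- Clinical care: Q5, "How likely are you to agree to share your identifiable PHYSICAL health data for your clinical care", then Q6, "How likely are you to agree to share your identifiable MENTAL health data for your clinical care".
- Structured research data: Q7 (physical), then Q8, "How likely would you be to share your de-identified MENTAL health data with the following".
- Free-text research data: Q9 (physical), then Q10, "How likely would you be to share your FREE TEXT de-identified MENTAL health data with the following".

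Within each pair the rows and the response scale are the same. The only randomisation described, in section 6.2 and in the survey just before Q5, is to one of three framing statements. Nothing in the Protocol says that question order is randomised or counterbalanced.

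**The concern.** Every respondent gives the mental answer second, directly after completing the same grid for physical data. The second answer may be influenced by the first: people may repeat a pattern, pull the second answer towards the first, or look for a difference because the question has been repeated. If so, the observed difference between the two grids mixes the effect of data type with the effect of position. A real difference could be hidden, or a difference could appear where none exists.

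Two things are at stake. One is the descriptive statement of whether people view the two kinds of data differently. The other is the level of primary measures (b), (d) and (f), which are only ever collected after a physical grid. The instrument fixes this order, so a statistical analysis plan cannot repair it: no respondent supplies data in the other order.

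**Working it through.** **1. The plan's own figure.** Section 6.1 gives power 0.9, three groups and f = 0.1, with n = 1,269. Alpha is not stated; 0.05 is assumed here. For a one-way ANOVA with df1 = 2, df2 = N - 3 and noncentrality N × f² = 1,269 × 0.01 = 12.69, power is 0.9001. At N = 1,266 it is 0.8994. The figure reproduces. It concerns the three framing arms and has no bearing on question order.

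**2. What can be estimated.** Take a linear model with seven terms: intercept, data type, position, two arm terms and two arm-by-type terms.

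- *Order as printed.* Position equals data type for every respondent, and the design has rank 6 of 7. The null vector is +0.707 on type, -0.707 on position and zero elsewhere. Type cannot be told apart from position, but the arm-by-type terms can still be estimated.
- *Counterbalanced order.* The rank is 7 of 7, so type and an additive position effect can both be estimated.

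**3. The framing comparison.** Let D be an arm's true mental-minus-physical difference and o a constant order effect. Each arm shows D + o. The difference between arms A and B is (D_A + o) - (D_B + o) = D_A - D_B, so o cancels. It would not cancel if framing changed the order effect itself.

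**4. Illustration of size.** The document gives neither an SD nor an order effect, so both are assumed. With no true difference, an additive effect o, a within-person difference SD s and SE = s/√n, the probability of a two-sided 5% rejection is Φ(o/SE - 1.96) + Φ(-o/SE - 1.96).

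| o (points) | n | s = 0.5 | s = 0.75 | s = 1.0 |
|---|---|---|---|---|
| 0.02 | 1,269 | 0.297 | 0.158 | 0.110 |
| 0.05 | 1,269 | 0.945 | 0.661 | 0.429 |
| 0.02 | 20,000 | 1.00 | 0.965 | 0.807 |
| 0.05 | 20,000 | 1.00 | 1.00 | 1.00 |

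Example: s = 1.0 and n = 1,269 give SE = 1.0/√1,269 = 0.0281 and o/SE = 0.05/0.0281 = 1.78, hence 0.429. A larger sample does not reduce the bias; it only narrows the interval around the biased value.

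**5. What counterbalancing cures.** Let M and P be the answers a person would give if each grid came first.

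- *Additive position effect o.* Physical-first shows (M - P) + o and mental-first shows (M - P) - o. The average is M - P, so the effect is removed.
- *Second answer pulled a fraction k towards the first.* Physical-first shows M - k(M - P) - P = (1 - k)(M - P). Mental-first shows M - P - k(M - P) = (1 - k)(M - P). The average is still (1 - k)(M - P), so the shrinkage remains. A symmetric exaggeration behaves the same way with the opposite sign.
- *First-asked grids only, compared between respondents.* The expected difference is M - P in both cases, because neither answer follows its paired grid. This holds cleanly only for Q5/Q6. By Q7 every respondent has already answered both kinds of grid.

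**6. Precision of the first-asked comparison.** With n/2 respondents per order and a single-answer SD σ, its SE is 2σ/√n. The within-person SE is σ√(2(1 - ρ))/√n, where ρ is the correlation between a person's two answers. The ratio is √(2/(1 - ρ)), which is at least √2 = 1.41 when ρ is not negative.

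**The case against.** The strongest reply is that harm is not shown. The SD and the order effect in the illustration are assumed, and 0.05 points on a five-point item is a small distortion. At n = 20,000 almost any trivial bias reaches significance, and pulling the second answer towards the first would shrink a difference rather than create one. All of this stands: the confounding is certain, while the size and direction of any bias are unknown.

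Prominence is also limited. The primary objective in section 2.1 is about views on sharing in general, section 6.3 lists separate levels of support, and neither names a mental-minus-physical main effect. The one formal objective that involves the contrast is the framing effect. A reader might infer that the study's headline result, or the randomised comparison, is compromised. The document does not support that: the comparison affected is a descriptive aim from sections 1 and 1.5, and a constant order effect cancels between arms.

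A reader might also infer that physical questions come first throughout the survey. They do not: the experience items put mental health (Q3) before physical health (Q4). Those items are predictors and not part of the contrast. All three framing statements also mention both kinds of health before Q5, so nobody meets the first grid unaware of the comparison. This may soften an order effect but does not separate it from data type.

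Finally, the consent item in section 4.2 warns that respondents may not all see the same questions or definitions. That is explained by framing and skip logic and says nothing about order.

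**Conclusion.** The point holds for the sharing questions Q5-Q10. Data type and position coincide for every respondent, so the descriptive mental-versus-physical contrast is conditional on physical-first order, and primary measures (b), (d) and (f) are observed only in second position. This conclusion is structural and needs no assumed values.

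Its practical size is unknown. The probabilities of about 0.43 to 0.95 at n = 1,269 and about 1.00 at n = 20,000 rest on an assumed within-person SD of 0.5 to 1.0, an assumed additive effect of 0.05 points and no true difference. They show how easily a small order effect could pass for a finding, not that one exists. The framing comparison is valid against a constant order effect, though it is estimated under one order only.

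This is an inexpensive design improvement to a stated descriptive aim, not a fault that undermines the study.

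**What to change.** In REDCap, randomise each respondent to physical-first or mental-first, crossed with the three framing arms (3 × 2), and keep that order across Q5-Q10. Include order and order-by-data-type in the model; the interaction carries the additive position effect. Report two estimates side by side:

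- the contrast averaged over the two orders, which removes an additive position effect but not a symmetric pull or exaggeration;
- the between-respondent comparison of the first-asked grids in Q5/Q6, which is free of carry-over from the paired grid.

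The cost is duplicated grids with branching logic, one more randomisation factor, and some extra build and testing. No respondent answers more questions. The between-respondent comparison is less precise than the within-person one.

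Appendix 3 refers to a live survey and section 4.4 fixes the closing date at 31 May 2020, so fielding may already be under way. If it is running as printed, leave the instrument alone, report the mental-versus-physical contrast as conditional on physical-first order, and state the limitation.
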